	Date Revised:	
	Study Number:	

Based on the above two options in the current opioid epidemic crisis, we propose to study the analgesic efficacy of liposomal bupivacaine to bupivacaine with dexamethasone as an adjuvant in interscalene block for shoulder surgeries. Till date, there is not study comparing the two.

1) Objectives:

Research Question:

Is the analgesic efficacy of liposomal bupivacaine superior to that of bupivacaine with dexamethasone as an adjuvant in interscalene block?

Primary Outcome: The primary outcomes is the time of analgesia duration (defined as the onset of sensory discomfort that required medication) and time of motor recovery (defined as the recovery of full motor function of both wrist and elbow on the nerve block side). Time to first analgesic request, NRS at 6 hours, 12 hours, 24 hours and 48 hours, POD 3, 4, 5, 6, 7 and total narcotic consumption.

Secondary Outcome: arm weakness (0 to 24 hours, 24 to 48 hours), arm numbness (0 to 24 hours, 24 to 48 hours), nausea, vomiting, dizziness, Horner's syndrome, hoarseness, dyspnea, Intra operative narcotic consumption, PACU and hospital length of stay, pain scores as assessed by PT on POD 1, and 2.

 Mount Sinai	Protocol Title:	COMPARISON OF THE ANALGESIC EFFICACY OF A SINGLE SHOT INTERSCALENE BLOCK WITH LIPOSOMAL BUPIVACAINE TO BUPIVACAINE WITH DEXAMETHASONE AS AN ADJUVANT-A RANDOMIZED CONTROLLED TRIAL
	Principal Investigator Name/Contact Info:	[name] MD. [name] [name]. [name] MD, PHD [name] MD [contact]
	Primary Contact Name/Contact Info	[name] MD. [contact]
	Date Revised:	
	Study Number:	

patient's satisfaction scores(Yes- I would prefer the same analgesic technique the next time or No-I would prefer a different analgesic technique) and quality of sleep (good, moderate/average, bad) on POD 0 and 1. Patient reported outcomes measurement information system (PROMIS) baseline global assessment will be conducted prior to surgery and post operative pain assessment at first follow up visit. Each patient will be assessed by standardized assessment of shoulder function as recommended by American association of shoulder and elbow surgery.

2) Background

See above. There have been several studies demonstrating efficacy of dexamethasone in prolonging the analgesic effect when administered both perineurally and intra-venously as an adjuvant to local anesthesia demonstrating a dose effect relationship.

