Once the primary team discharges the patient, a telephone follow - up every day until resolution of any residual arm weakness/numbness will be done by the anesthesia resident originally involved in the surgery.

Patients will also be asked to note the time to first analgesic request in addition to onset of sensory discomfort and motor recovery.

a) Recruitment Methods

See above. With the HIPAA waiver requested, the surgeon will provide investigators (both of whom are physicians within the department of Anesthesiology) with information of eligible patients. After the operating room schedule has been reviewed for potential participants in the study the contact information will be obtained through the surgeon's office. Subjects will be called by the department of Anesthesiology when their surgery is scheduled, and they will be informed about the study then.

 Mount Sinai	Protocol Title:	COMPARISON OF THE ANALGESIC EFFICACY OF A SINGLE SHOT INTERSCALENE BLOCK WITH LIPOSOMAL BUPIVACAINE TO BUPIVACAINE WITH DEXAMETHASONE AS AN ADJUVANT-A RANDOMIZED CONTROLLED TRIAL
	Principal Investigator Name/Contact Info:	[name] MD. [name] [name]. [name] MD, PHD [name] MD [contact]
	Primary Contact Name/Contact Info	[name] MD. [contact]
	Date Revised:	
	Study Number:	

b) Inclusion and Exclusion Criteria

Inclusion criteria: All patients between age 18-75 years undergoing primary shoulder arthroscopic procedure. All patients who speak read and understand English will be included for follow up purposes.

Exclusion criteria included patients with patient refusal, ASA 5, presence of coagulopathy, severe lung disease, contralateral diaphragmatic palsy, insulin-dependent diabetes, hepatic disease/failure, kidney disease/failure, pregnancy, chronic opioid use (defined as opioid use for >3 months), or allergy to any of the study medications.

c) Number of Subjects

N= 100, recruit ability is manageable. Based on previous study conducted by Tandoc et al with estimated average duration of analgesia at 22 hours with dexamethasone in 0.5% bupivacaine and assumed average SD of 3 hours, they estimated that 16 patients would be needed to provide 80% power to conclude absence of effect at the significance level of 0.05 among treatment groups. To allow for 20% patient dropouts, 30 subjects per group will be targeted for enrollment.

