Data will be expressed as mean \pm SD or median with interquartile range as appropriate. Categorical data will be analyzed with Fisher exact test and chi-square test. The duration of analgesia and motor block will be analyzed by the Kaplan-Meier survival analysis and Cox

 Mount Sinai	Protocol Title:	COMPARISON OF THE ANALGESIC EFFICACY OF A SINGLE SHOT INTERSCALENE BLOCK WITH LIPOSOMAL BUPIVACAINE TO BUPIVACAINE WITH DEXAMETHASONE AS AN ADJUVANT-A RANDOMIZED CONTROLLED TRIAL
	Principal Investigator Name/Contact Info:	[name] MD. [name] [name]. [name] MD, PHD [name] MD [contact]
	Primary Contact Name/Contact Info	[name] MD. [contact]
	Date Revised:	
	Study Number:	

proportional hazards modeling. Subgroup pairwise analyses will be conducted via Kruskal-Wallis rank test with Bonferroni correction for significance. All analysis will be conducted with intent-to-treat approach to minimize the potential effects of dropout. Statistical significance will be defined as $P<0.05$.

d) Study Timelines

2018-2019 and subsequent data analysis. The subject's participation will be from time of enrollment to complete resolution of arm weakness and motor strength. Estimated date of enrollment completion will be when 100 eligible subjects are enrolled in final data analysis. Estimate date for study completion will be June 2019.

e) Study Endpoints

Primary end point will be the time of first analgesic request for the first 24 hours post operatively.

Secondary end points will be NRS at 6 hours, 12 hours, 18 hours, 24 hours, 36 hours and 48 hours and oxycodone use.

f) Procedures Involved in the Human Research

Prospective randomized controlled trial and data analysis only.
Ultrasound guided interscalene block with nerve catheter placement.

 Mount Sinai	Protocol Title:	COMPARISON OF THE ANALGESIC EFFICACY OF A SINGLE SHOT INTERSCALENE BLOCK WITH LIPOSOMAL BUPIVACAINE TO BUPIVACAINE WITH DEXAMETHASONE AS AN ADJUVANT-A RANDOMIZED CONTROLLED TRIAL
	Principal Investigator Name/Contact Info:	[name] MD. [name] [name]. [name] MD, PHD [name] MD [contact]
	Primary Contact Name/Contact Info	[name] MD. [contact]
	Date Revised:	
	Study Number:	

g) Specimen Banking

N/A

h) Data Management and Confidentiality

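### Arm weakness and numbness are listed in two 24-hour windows with no scoring rule; read as any-in-window, the 0–24 h items cannot compare duration, and numbness has no time-to-resolution outcome

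*Combined protocol and SAP*

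**What the plan says.** Section 1 (Objectives, Secondary Outcome) lists "arm weakness (0 to 24 hours, 24 to 48 hours), arm numbness (0 to 24 hours, 24 to 48 hours"), next to nausea, vomiting, dizziness, Horner's syndrome, hoarseness and dyspnea. It does not say whether the items are yes/no, graded or timed, when in the window they are assessed, or what counts as positive.

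The Primary Outcome paragraph of the same section includes "time of motor recovery (defined as the recovery of full motor function of both wrist and elbow on the nerve block side"). No corresponding outcome exists for numbness.

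Section 5 (Study Design) gives every patient an interscalene block before surgery. After discharge there is a daily telephone call "until resolution of any residual arm weakness/numbness will be done by the anesthesia resident originally involved in the surgery". It adds: "Patients will also be asked to note the time to first analgesic request in addition to onset of sensory discomfort and motor recovery". The time at which numbness resolves is not among these.

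The analysis paragraph in section 5c (Number of Subjects) states: "Categorical data will be analyzed with Fisher exact test and chi-square test". It continues: "The duration of analgesia and motor block will be analyzed by the Kaplan-Meier survival analysis and Cox" proportional hazards modelling. The only duration in the documents is also in section 5c: "estimated average duration of analgesia at 22 hours with dexamethasone in 0.5% bupivacaine and assumed average SD of 3 hours". No rate, power or sample size is given for weakness or numbness.

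**The concern.** Weakness and numbness matter here because of how long they last, and earlier discharge is one of the plan's stated aims. Two broad windows are a poor measure of duration if the items record presence.

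- **0–24 h.** Every patient is blocked at the start of this window. Weakness or numbness at some point in it shows that the block took, not how long it lasted. A non-significant comparison could be reported as no difference in weakness or numbness when the item could hardly have shown one.
- **24–48 h.** Once the block has worked, being positive means recovery later than 24 h. A block that ends at 24.5 h counts the same as one that ends at 47 h. For weakness, a finer measure is already planned. For numbness, none is, so duration would be compared only through this cut.

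**Working it through.** **Inputs.** From section 5c: mean 22 h and SD 3 h (for duration of analgesia), 80% power, alpha 0.05, and 30 per group. N = 100 appears in the same section and means 50 per group if allocation is 1:1. The two totals disagree, which is a separate matter, so both sizes are shown. Assumed, because the documents do not give them: yes/no scoring, the 0–24 h rates, normally distributed recovery times with the analgesia mean and SD, and the difference between groups.

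**The plan's own figure.** Section 5c reports that "they estimated that 16 patients would be needed to provide 80% power to conclude absence of effect at the significance level of 0.05" but states no difference, so 16 cannot be derived from the stated inputs. Reading it as per group, two-sided, and solving n = 2·SD²·(1.96 + 0.84)²/d² for d gives d = 3·2.80·√(2/16) ≈ 2.97 h. A difference of about 3 h is therefore the nearest thing to an implied effect. Both 2 h and 3 h are examined below.

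**0–24 h items.** If one group is 100% positive and the other has k negatives among n, the two-sided Fisher p-value is 2·C(n,k)/C(2n,k).

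| n per group | k = 5 | k = 6 |
|---|---|---|
| 30 | 0.052 | 0.024 |
| 50 | 0.056 | 0.027 |

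Significance needs at least 6 patients in the other group with no weakness (or no numbness) at any time in the first 24 h: 6/30 = 20% or 6/50 = 12%. If every patient in both groups is positive, power is zero. Exact Fisher power at assumed rates near the ceiling:

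| Rates | 30 per group | 50 per group |
|---|---|---|
| 95% v 99% | 0.2% | 2% |
| 90% v 98% | 4% | 19% |
| 90% v 99% | 6% | 27% |

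**24–48 h items.** A patient is positive if recovery time T exceeds 24 h, so P(T > 24) = 1 − Φ((24 − mean)/3). This is 25.2% for a mean of 22 h, 50.0% for 24 h and 63.1% for 25 h. Power of the yes/no item (exact Fisher) against a t-test on hours:

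| Means | Yes/no, 30 | Yes/no, 50 | Hours, 30 | Hours, 50 |
|---|---|---|---|---|
| 22 v 24 h | 40.5% | 66.5% | 71.9% | 91.0% |
| 22 v 25 h | 79.1% | 96.4% | 96.8% | 99.9% |
| 18 v 21 h | 21% | 53% | 96.8% | 99.9% |
| 20 v 23 h | 65% | 90% | 96.8% | 99.9% |
| 24 v 27 h | 75% | 95% | 96.8% | 99.9% |

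The plan would use survival methods rather than a t-test. Simulation of 1,500 trials for 22 v 24 h put log-rank power at about 65% and 85%. That is below the t-test but still well above the yes/no item. The loss from the cut is present in every row. Its size depends on the difference and on how far mean recovery lies from 24 h.

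**The case against.** - **Scoring is not stated.** A graded score, or hours of weakness within 0–24 h, need not reach a ceiling. This stands: yes/no is a reading, supported by the neighbouring items and by the Fisher/chi-square rule for categorical data, but not written in the plan. If the reading is wrong, the items still lack a scale, an assessment time and a criterion for positive.
- **Duration of weakness is already covered.** Motor recovery time is listed as primary, noted by patients and analysed by Kaplan-Meier and Cox. The 24–48 h weakness item supplements that analysis and takes no power from it. This largely stands, although motor recovery is defined at wrist and elbow only. It does not help numbness.
- **No power is claimed for these outcomes.** They are secondary, and the research question is analgesic efficacy. This stands, and makes the point a modest one.
- **A reader might infer that the 24–48 h items are underpowered.** The documents do not support that in general. A 2 h difference appears nowhere in them, and at the roughly 3 h that fits the figure of 16, the item has 79.1% or 96.4% power.
- **A reader might also infer that both 24–48 h items merely repeat a time already recorded.** That is approximately right for weakness and wrong for numbness, for which no resolution time is recorded.

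**Conclusion.** The point holds in a limited form. The firm findings from the text are that the four items have no scoring rule and that numbness has no time-to-resolution outcome, even though follow-up runs until it resolves. On the any-in-window reading, the 0–24 h items say almost nothing about duration: with one group at 100%, the other would need 20% (n = 30) or 12% (n = 50) negatives to reach significance. On the same reading, the 24–48 h items discard information. If motor block and numbness share the analgesia mean and SD, that costs about 31 or 25 percentage points of power against hours for a 2 h difference (71.9 − 40.5; 91.0 − 66.5), and about 18 or 4 points for 3 h (96.8 − 79.1; 99.9 − 96.4). None of this touches the main analgesic comparison. It is an inexpensive improvement to secondary outcomes, worth making chiefly for numbness and to prevent an uninformative null result from being read as equivalence.

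**What to change.** - **Section 5 (Study Design):** add the time at which numbness resolves to the times patients are asked to note, and confirm it at the existing daily calls. Carry it into the list of recorded data in section 5h.
- **Section 1:** state the scale, assessment time and criterion for positive for arm weakness and numbness. Add duration of numbness as a secondary outcome, and rely on motor recovery time for duration of weakness.
- **Section 5c, analysis paragraph:** analyse duration of numbness by Kaplan-Meier and Cox, as for motor block. Report weakness and numbness still present at 24 h and at 48 h as descriptive percentages. Do not test the 0–24 h items between groups; any occurrence in 0–24 h may be kept as a description of block success.

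**Cost:** wording and one extra recorded time, with no added visits, calls or patients. The downside is precision. If the patient does not note the time, it is known only to lie between two daily calls, about a day apart. It should then be treated as interval-censored, and part of the gain over the yes/no item is lost.

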	Principal Investigator Name/Contact Info:	[name] MD. [name] [name]. [name] MD, PHD [name] MD [contact]
	Primary Contact Name/Contact Info	[name] MD. [contact]
	Date Revised:	
	Study Number:	

patients will be randomized using computer generated tables and sealed envelopes. A designated resident not involved in the study will open the sealed envelope and randomize the patient into the following groups:

Group A—Liposomal bupivacaine(133mg bupivacaine diluted normal saline total 25cc)

Group B---Dexamethasone 4mg in 0.5% Bupivacaine 25cc

The patients will be transferred to the OR to proceed with the surgery. Standard ASA monitors will be placed again and after pre oxygenation, general anesthesia will be induced with propofol and fentanyl. Laryngeal mask airway of appropriate size will be inserted and patient will be connected to the ventilator for the procedure. Maintenance of anesthesia will be achieved with sevoflurane and oxygen/air mixture. Once the procedure is completed, patients will be extubated and transferred to the recovery room(PACU) for post anesthetic care.

The patient will also receive 4mg of ondansetron intra-venous in the OR as prophylaxis for post operative nausea and vomiting.

Patients, attending anesthesiologists, surgeon and research assistant collecting the data will be blinded of the group assignment. The medication solution will be prepared by the resident physician.

 Mount Sinai	Protocol Title:	COMPARISON OF THE ANALGESIC EFFICACY OF A SINGLE SHOT INTERSCALENE BLOCK WITH LIPOSOMAL BUPIVACAINE TO BUPIVACAINE WITH DEXAMETHASONE AS AN ADJUVANT-A RANDOMIZED CONTROLLED TRIAL
	Principal Investigator Name/Contact Info:	[name] MD. [name] [name]. [name] MD, PHD [name] MD [contact]
	Primary Contact Name/Contact Info	[name] MD. [contact]
	Date Revised:	
	Study Number:	

Pain scores in the form of NRS (NUMERICAL RATING SCALE) will be assessed on arrival to PACU. Pain scores will also be assessed 1 hour after arrival to PACU and at the time of discharge from PACU. NRS scores will be assessed on the floors every 6 hourly during the first 24 hours, 8 hourly and then every 12 hourly during the second 24 hours. If NRS scores are more than 5 at any time a one-time dose of oxycodone 10mg and Tylenol 1000 mg will be given.

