Data collected in excel file to be de-identified after initial collection. Excel file be subsequently encrypted and shared only between the two above listed investigators via secure Mt. Sinai (chpnet) electronic mail.

The information included in the data will be medical record number, age, gender, ASA class, type of surgery, pain score assessments, duration of surgery, anesthesia time, time to first narcotic, total narcotic use and pain scores up to 48 hours after surgery. In case of known history of type 1 or 2 diabetes, preoperative and post operative finger stick will be recorded. Time of administration of study drug, smoking status and patient satisfaction scores will also be recorded. Only the research personnel will have access to the data. The data will be stored as a hard copy files and on a secure spreadsheet. The research personnel are responsible for the receipt of the data. The PI will keep the hard copies secure and any electronic data will be encrypted. No personal identifiers will be used. The data will undergo statistical analysis.

i) Provisions to Monitor the Data to Ensure the Safety of subjects

 Mount Sinai	Protocol Title:	COMPARISON OF THE ANALGESIC EFFICACY OF A SINGLE SHOT INTERSCALENE BLOCK WITH LIPOSOMAL BUPIVACAINE TO BUPIVACAINE WITH DEXAMETHASONE AS AN ADJUVANT-A RANDOMIZED CONTROLLED TRIAL
	Principal Investigator Name/Contact Info:	[name] MD. [name] [name]. [name] MD, PHD [name] MD [contact]
	Primary Contact Name/Contact Info	[name] MD. [contact]
	Date Revised:	
	Study Number:	

Part I: Elements of Data and Safety Monitoring Plan

MSSM Principal Monitor:

Last Name: [name]

First Name: [name]

Academic Title: Attending Physician, Professor

Department: Anesthesiology

Mailing Address: Mount Sinai West [name]

[contact]

Fax:

E-mail: [contact]

MSSM Principal Monitor:

Last Name: [name]

First Name: [name]

Academic Title: Attending Physician, Assistant Professor

Department: Anesthesiology

Mailing Address: Mount Sinai West [name]

[contact]

Fax:

E-mail: [contact]

Last Name: [name]

First Name: [name]

Academic Title: Attending Physician, Professor

Department: Orthopedics

Mailing Address: Mount Sinai West [name]

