As with any medication, there is a possibility of an allergic reaction. Although rare, possible complications include LA toxicity, hypersensitivity reaction, bleeding or local site infection, chance of pneumothorax. All anesthesiologists involved in patient care will be prepared for the prevention and rescue for any complications involving local anesthetic injections.

7) Provisions for Research Related Injury

If patients are injured or made sick from taking part in this research study, medical care will be provided. Generally, this care will be billed to the patient or their insurance in the ordinary manner and the patient will be

 Mount Sinai	Protocol Title:	COMPARISON OF THE ANALGESIC EFFICACY OF A SINGLE SHOT INTERSCALENE BLOCK WITH LIPOSOMAL BUPIVACAINE TO BUPIVACAINE WITH DEXAMETHASONE AS AN ADJUVANT-A RANDOMIZED CONTROLLED TRIAL
	Principal Investigator Name/Contact Info:	[name] MD. [name] [name]. [name] MD, PHD [name] MD [contact]
	Primary Contact Name/Contact Info	[name] MD. [contact]
	Date Revised:	
	Study Number:	

responsible for all treatment costs not covered insurance, including deductibles, co-payments and coinsurance. This does not prevent the patient from seeking payment for injury related to malpractice or negligence. Contact the investigator for more information.

8) Potential Benefits to Subjects

It is important to know that you may not get any benefit from taking part in this research. Others may not benefit either. However, possible benefits may be improved knowledge about how the addition of adjuvant to local anesthesia affects pain control in shoulder surgery. There is potential for better pain control after the surgery.

9) Provisions to Protect the Privacy Interests of Subjects

Patients will be appropriately educated about the research study. Any questions or concerns they have will be adequately addressed and patients will have the option to decline participation. Patients will be given as much time as they need to review the consent form. The study personnel will be approaching the subjects. Privacy will be maintained by not including any identifiers such as names or addresses in the data collected.

The identities of human subjects whose data is being studied will be de-identified as per HIPAA Privacy Rule.

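### In the available text, the six harms named as secondary outcomes have no time window and no stated assessment, so no event cannot be told from not asked

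*Combined protocol and SAP*

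**What the plan says.** The secondary outcomes in section 1 (Objectives) include "nausea, vomiting, dizziness, Horner's syndrome, hoarseness, dyspnea". No window, definition or assessor is attached to them. The items just before them in the same sentence do have windows: "arm weakness (0 to 24 hours, 24 to 48 hours), arm numbness (0 to 24 hours, 24 to 48 hours".

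Section 5 (Study Design) sets out the contacts. NRS pain is taken on arrival in PACU, and "Pain scores will also be assessed 1 hour after arrival to PACU and at the time of discharge from PACU". After that, "NRS scores will be assessed on the floors every 6 hourly during the first 24 hours", with further NRS scores in the second 24 hours. After discharge there is "a telephone follow - up every day until resolution of any residual arm weakness/numbness", made by the anesthesia resident who took part in the surgery. Patients are asked to note when they first request analgesia, when sensory discomfort begins and when motor function returns. Outside section 1, the available text mentions nausea and vomiting as postoperative events only as the target of prophylaxis: "4mg of ondansetron intra-venous in the OR as prophylaxis for post operative nausea and vomiting".

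Section 5e gives NRS from 6 to 48 hours and oxycodone use as secondary end points. The data list in section 5h covers patient and surgery characteristics, "duration of surgery, anesthesia time, time to first narcotic, total narcotic use and pain scores up to 48 hours after surgery", finger sticks in patients with diabetes, study drug time, smoking and satisfaction.

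Safety oversight is general. Section 4 gives the lead investigator responsibility for safety monitoring and for responding to adverse events, and says a safety monitoring board will be formed.

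**The concern.** The six harms are the tolerability side of a comparison that section 1 introduces as not previously studied. Several of them are short-lived. An effect that was present in PACU and not asked about cannot be recovered later.

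The statistical text in section 5c sends categorical data to Fisher's exact and chi-square tests. It does not name the harms, but yes/no harms would naturally fall there, and such tests need a recorded answer for each patient. If harms enter the data only when someone happens to chart or mention them, the denominator is unknown and a report of similar tolerability may only show that nobody asked.

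There is also a route to unequal ascertainment. Contact after discharge ends when weakness and numbness resolve, and time to motor recovery is itself one of the primary outcomes in section 1. If one arm's blocks last longer, that arm gets more calls and more chances to mention a harm.

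**Working it through.** The plan gives no rate or power figure for these harms, so there is nothing of its own to reproduce. The main check sets the six harms against every place where the available text says something is measured or recorded.

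- PACU contacts (section 5; arrival, 1 hour, discharge): pain score only. Harms included: 0 of 6.
- Floor contacts (section 5): NRS only. 0 of 6.
- Telephone calls after discharge (section 5): arm weakness and numbness. 0 of 6, and the calls stop on resolution.
- Patient-noted items (section 5): analgesic request, sensory discomfort, motor recovery. 0 of 6.
- Secondary end points (section 5e): NRS and oxycodone use. 0 of 6.
- Data list (section 5h): 0 of 6.

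**How much weight section 5h can bear.** The same list leaves out time of motor recovery (a primary outcome that patients are asked to note), arm weakness and numbness (which the calls follow), sleep quality, length of stay, PROMIS and the shoulder function score. Its pain scores stop at 48 hours, although section 1 lists NRS to POD 7. It is therefore not a complete list, and absence from it does not by itself show that an item will not be collected. The stronger evidence is that no contact is said to ask about the harms.

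**Why the number asked matters.** If no event is recorded among *m* patients who were all asked, the one-sided 95% upper bound on the true rate is 1 − 0.05^(1/*m*). Taking 100 patients split equally (an assumption), there are 50 per arm.

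- All 50 asked: 1 − 0.05^(1/50) = 5.8%.
- Only 25 of the 50 asked (assumed): 1 − 0.05^(1/25) = 11.3%.
- Number asked unknown: no bound can be stated.

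**Power, as an illustration only.** The event rates below are assumptions and come from nowhere in the documents. Power is the sum, over all pairs of event counts (x, y), of Bin(x; 50, p1) × Bin(y; 50, p2) for the pairs where the two-sided Fisher test gives P < 0.05. Incomplete capture multiplies both rates by the captured fraction.

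| Assumed rates, 50 per arm | All events captured | 75% captured |
|---|---|---|
| 35% vs 10% | 82% | 63% |
| 20% vs 10% | 20% | 12% |
| 10% vs 5% | 6% | 4% |

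For 35% vs 10%, power falls to 37% if half the events are captured. In that case the recorded rates are 17.5% and 5%, so the risk difference halves from 25 to 12.5 percentage points while the ratio stays at 35/10 = 17.5/5 = 3.5. Equal under-capture therefore shrinks the difference but not the ratio. Unequal capture between arms would distort both.

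**The case against.** The strongest objection is that the part of the document most likely to describe adverse-event recording could not be read. The text following the opening of the monitoring plan in section 5i was not available, nor was part of section 4. That stands, and the finding is limited accordingly. The section 5 contacts and the 5e and 5h lists can be read, and they do not mention the harms.

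A reader might infer that the harms will be missing from the trial altogether. The documents do not support that. The harms are named outcomes, a blinded research assistant collects data, the investigator has a safety role and a board is planned. Some events would be charted or volunteered. What is absent from the available text is a question, a time point and a window.

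A reader might also infer that sections 1 and 5h contradict each other on whether harms are in the dataset. Section 5h does not claim to be complete and also omits a primary outcome, so it shows poor alignment with section 1 and not a decision to leave harms out.

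A third tempting reading is that the gap costs the trial a known amount of power, such as the fall from 82% to 37%. That depends on assumed rates of 35% and 10%. At 20% vs 10%, power is only about 20% with perfect recording, so better capture would not make the trial able to compare such harms by a significance test. The gain lies in interpretable counts and denominators.

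Finally, these are secondary outcomes in a trial whose stated question is analgesic efficacy. That limits the weight of the point but does not remove it, because unprompted transient events cannot be recovered afterwards.

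**Conclusion.** The point holds for the text available. The six harms have no window and appear in 0 of 6 visible places of collection or listing. Followed as written, they would be captured by unprompted report or routine charting. A blank could not be read as no event, and the opportunity to report after discharge could differ between arms if block duration does.

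The conclusion rests on two conditions: that the unavailable text holds no schedule for asking about these harms, and that staff do what section 5 describes and no more. That capture would differ by arm is a possibility created by the stopping rule for the calls and is not shown by any figure in the documents. No loss of power can be derived, because no event rates are given. The change should be made, but the point does not affect the trial's primary comparison.

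**What to change.** 1. In section 5, add a prompted yes/no for each of the six harms at the contacts already used for NRS: PACU arrival, 1 hour, PACU discharge, and the 6 to 48 hour NRS time points.
2. In hospital, the blinded research assistant records the answers. For patients already discharged, the same scripted questions are put at the existing NRS or telephone contact and continue through 48 hours whether or not the block has resolved. The script matters because section 5 gives the calls to the resident, who is not among those listed as blinded.
3. Define each outcome in section 1 as any occurrence from injection to 48 hours, the same window for every patient. Add the fields to section 5h and bring section 5e into line.
4. Report number with the event over number assessed, by arm, with the risk difference and 95% CI. Give no power figure for these outcomes unless the assumed rates are stated and shown over a range.

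The cost is a wording change, six fields on the form and about a minute per contact. Patients who go home early and whose block resolves early may need calls continued to 48 hours, so the change is not entirely free of extra contact. Reported event rates will probably be higher than with spontaneous charting. The change concerns measurement only.
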